Discomfort resulting from study questionnaires	1. All participants will be informed that they may take a break at any time from questionnaires and that study staff are available to discuss issues that warrant follow up.	This risk has not been reported.
Confidentiality of participant identity	1. Because doctors in some states are required to report any mental health condition that may affect their performance to the state licensing board, we have submitted a request to the FDA for a Certificate of Confidentiality.	No prior studies have had participant inclusion criteria that specify doctors and nurses.
Reproductive risks	1. All female potential participants will be asked about their menopausal status at screening, and pre-menopausal participants will undergo a pregnancy test.	As noted above, the reproductive risks seem minimal, although they are not well characterized.
Length of study for subjects who were taking medications prior to study entry and who are randomized to placebo	1. The study team will clearly communicate with potential subjects during consent conversations to ensure eligible subjects know they may be off their medications longer if they are assigned the placebo group and then chose the open-label psilocybin session following un-blinding. We will recommend that individuals taking medications that need to be stopped, discuss this with their provider(s), family, and any other trusted people, prior to agreeing to participate in the study.	This risk has not been reported.
	2. Minimize the time for subjects who are randomized to the placebo group to an open-label psilocybin session. We anticipate that arranging and scheduling an open-label psilocybin session will take 1-2 weeks. During this time, subjects will be followed weekly and will have an additional preparation psychotherapy session, and every weekly contact will include administration of the C-SSRS suicidality screen to minimize risk to these subjects. We judge that this additional risk of 1-2 weeks off antidepressants is acceptable given	

Page 13 Version 1.16, July 18, 2022

that these subjects will be monitored closely.	

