3.1.4. Study Research Evaluations and Procedures

Medication and lifestyle changes may be required of all participants. All participants will be required to taper off and discontinue use of antidepressants (such as SSRIs) before starting the study and cannot take antidepressants during the study even if they were taking them before study entry. Participants who were taking antidepressants before

study entry will need to be off them for five half-lives of the drug plus 2 weeks before starting the study and will be required to stay off their medication until after they have completed the primary outcome measurements on day 28. After unblinding (as early as day 28, after primary outcome measurements are received). Subjects who were randomized to psilocybin will be able to resume antidepressants in consultation with their provider. Subjects who were randomized to placebo will need to stay off their antidepressants if they wish to have an open-label psilocybin medication session, and after their open-label psilocybin session they will need to stay off their medication until at least day 29 post-open-label-psilocybin, until after they have completed the day 28 post-open-label-psilocybin outcome measurements. If a participant randomized to placebo does not wish to have an open-label psilocybin medication session, they will be able to resume their antidepressants after their primary outcome measurements in consultation with their provider, as early as day 29 post-open-label-psilocybin. They will also need to abstain from tobacco products, alcohol, or any recreational drugs such as marijuana during the study. Study personnel may obtain a release to contact the participant's prescribing provider to discuss current prescriptions and medication history. This is decided on a case by case basis upon the discretion of the PI.

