6.1. Randomization Blinded Study Phase

Upon completion of the Preparation sessions, participants will be assigned to one of the two conditions for the Medication Dosing session: the experimental condition (synthesized psilocybin 25mg) or placebo (niacin). The randomization will be performed by IDS and capsules will be placed in envelopes for each participant. Randomization will be stratified by profession (physician vs nurse) and ethnicity (Black or Hispanic vs other).

Psilocybin and niacin will be administered in identically appearing opaque, size 0 gelatin capsule with approximately 180ml of water. The dose of psilocybin will be 25 mg and the niacin will be 100 mg. Each participant will have the option of participating in the medication dosing sessions. In the study, half of the participants will be randomized to receive psilocybin (n=15) or the placebo, niacin (n=15). Following the first treatment session of either the active agent or placebo, participants who were randomized to receive placebo will be offered the option to receive open-label psilocybin. (The blind will be broken at 4weeks to make this determination, after primary endpoint measures have been collected. Clinical raters will remain blind to the treatment assignment). Data will be collected from all subjects after open-label treatment for descriptive purposes, but these data will not be analyzed as part of our primary analysis plan.

The participant's condition assignment will be maintained from randomization until the 4 week unblinding. If there is an adverse event or other emergency requiring knowledge of participant's condition assignment, as when pharmacological intervention is necessary, the blind may be broken for an individual participant. In this case, the study raters who will administer the questionnaires will remain blind to the participant's condition assignment.

Participants in the placebo condition will be eligible for an open-label study continuation. They will be re-screened after the blind is broken to make sure they still meet study criteria. If they are eligible and choose to enroll in the open-label continuation, they may do so, undergoing psilocybin-assisted sessions occurring within another seven to 14-day period.

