6.2.5. Long-term follow-up

A study therapist who conducted the integration, medication dosing and preparation sessions will contact the participant at 3 months post-psilocybin, and 6 months post-psilocybin

(note that this takes into account participants who receive psilocybin after the primary endpoint measures have been collected in the open label phase of the study (see below). The therapist will have a 30 min phone call or video call with the participant, and the participants will fill out measures using a secure online portal.

6.2.6. Timing and Location of Meetings, Sessions, and Measures.

Although much effort is put in to scheduling participants within the stated time frames, these are only estimates. Variables out of the study team's control (e.g., participant availability, university closings, availability of study rooms, illness) may prevent the scheduling of volunteers within the stated time frame goals. There is no evidence to suggest that the difference in timing of sessions, meetings, and measures will adversely affect the volunteer or the validity of the study. On those occasions when the timing of meetings, sessions or measures deviate substantially from the time frames in the protocol, we will report these as deviations in the Continuing Review.

6.3. Open Label Psilocybin Sessions.

The participants who choose to receive open-label psilocybin will be re-screened after the blind is broken after primary endpoint measures are collected (week 4) to make sure they still meet study criteria. If they are eligible and choose to enroll in the open-label continuation, they may do so, undergoing a psilocybin-assisted session occurring within another seven to 14-day period.

The open-label phase of the study will follow nearly identical procedures to those used in the randomized phase except that a single preparation psychotherapy session will be given (see Schedule below, Study day -1). Participants will be re-assessed on all study measures following the same schedule of the randomized phase.

Participants need not complete any portion of the open-label phase or the several follow up support appointments for their participation in the study to be considered completed.

Data will be collected from all subjects after open-label treatment for descriptive purposes and will be viewed not as part of our primary analysis plan but as part of a secondary analysis examining the impact of PAP on symptoms of depression and burnout.

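### The risk table accepts 1-2 weeks of extra time off antidepressants for niacin participants who take open-label psilocybin, but the protocol's own restart rule makes it about 5-6 weeks

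*Combined protocol and SAP*

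**What the plan says.** The last row of the risk table in section 1.3.3.8 deals with participants who were taking medication before entry and are randomized to placebo. Its first item says candidates will be told that "they may be off their medications longer if they are assigned the placebo group and then chose the open-label psilocybin session following un-blinding". Its second item says "We anticipate that arranging and scheduling an open-label psilocybin session will take 1-2 weeks", describes weekly follow-up, an extra preparation session and suicidality screening during that time, and concludes: "We judge that this additional risk of 1-2 weeks off antidepressants is acceptable given" the close monitoring.

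Sections 6.1 and 6.3 both put the open-label session 7 to 14 days out, after unblinding and re-screening: "undergoing psilocybin-assisted sessions occurring within another seven to 14-day period" in 6.1, and the same window in 6.3.

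Section 3.1.4 sets the restart rules:

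- Everyone stays off antidepressants until the Day 28 primary measurements are done.
- Psilocybin arm, after unblinding, which can be as early as Day 28: "Subjects who were randomized to psilocybin will be able to resume antidepressants in consultation with their provider".
- Niacin arm, declining open-label: "they will be able to resume their antidepressants after their primary outcome measurements in consultation with their provider". The clause then gives the earliest day as day 29 counted from an open-label dose.
- Niacin arm, taking open-label: they stay off while waiting, and "after their open-label psilocybin session they will need to stay off their medication until at least day 29 post-open-label-psilocybin", once the day 28 measures after that dose are complete.

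**The concern.** The row names its risk as being off medication for longer and expresses the accepted quantity as time off antidepressants. The figure attached to it, however, is the scheduling wait. The restriction in section 3.1.4 does not end at the open-label dose; it runs about four more weeks, and the row's figure leaves those weeks out.

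This row is the protocol's explicit acceptance of extra antidepressant-free time for a group enrolled with moderately severe symptoms that persisted despite treatment (section 4.1). Those who stopped an antidepressant have already been through a washout of five half-lives plus 2 weeks and the 28-day blinded phase. If the figure is wrong, the risk has been accepted for a much shorter interval than the protocol imposes. The row also calls for a consent conversation on this point, and any duration given there should be the right one.

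**Working it through.** This is a day count, with day 0 as the randomized dose.

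**Inputs**

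- Wait from unblinding to the open-label session: 7-14 days (sections 1.3.3.8, 6.1 and 6.3), taken to start on Day 28.
- Restriction after the open-label dose: until at least day 29 (section 3.1.4).
- Restart without open-label: Day 28 for the psilocybin arm. For niacin participants who decline, the stated day cannot apply because they have no open-label dose to count from. It is read here as Day 29 of the randomized phase, which is an assumption. Both values are carried through.

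**The plan's figure.** The wait alone is 7/7 = 1 week to 14/7 = 2 weeks. This reproduces the stated 1-2 weeks exactly, and no other term is in it.

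**Earliest restart with open-label** = 28 + wait + 29

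- 7-day wait: 28 + 7 + 29 = day 64
- 14-day wait: 28 + 14 + 29 = day 71

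**Additional time off** = restart with open-label minus restart without

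| Wait | Comparator Day 28 | Comparator Day 29 |
|---|---|---|
| 7 days | 64 - 28 = 36 days | 64 - 29 = 35 days |
| 14 days | 71 - 28 = 43 days | 71 - 29 = 42 days |

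The range is 35-43 days, or 35/7 = 5.0 to 43/7 = 6.1 weeks.

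**Against the stated figure**

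- Ratio: for the 7-day wait, 35/7 = 5.0 and 36/7 = 5.1; for the 14-day wait, 42/14 = 3.0 and 43/14 = 3.1.
- Share covered: from 7/36 = 19% to 14/42 = 33%.

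**Sensitivity**

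- Zero wait: 28 + 0 + 29 = day 57, so 57 - 29 = 28 or 57 - 28 = 29 extra days, against a stated maximum of 14.
- Restart allowed on day 28 after the open-label dose instead of day 29: each result falls by one day, so the lower end becomes 34 and a zero wait gives 27-28. Section 3.1.4 says at least day 29, so 35-43 is the direct reading.

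No combination gives 1-2 weeks as the total additional time off antidepressants.

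**The case against.** The strongest reply is that the row means only the wait. Its second item is about shortening the time to the open-label session, and the monitoring it describes and the risk it judges both point back to that period. On this reading the 1-2 weeks is the extra time with neither antidepressant nor study treatment. Afterwards the participant has had 25 mg of psilocybin and integration sessions, and is restricted in the same way as someone randomized to psilocybin.

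That explains where the figure came from, but it does not rescue the sentence. The first item names the risk as longer time off medication, and the judgement is worded as time off antidepressants. The row does not argue that having received psilocybin makes the later weeks acceptable, and whether psilocybin helps in this population is what the trial is testing.

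Several other points do stand:

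- The 7-14 days is not itself miscalculated; the fault is that it is used for a longer interval.
- Section 3.1.4 states the full restart rule, so the true interval can be worked out. The consent form is not among the documents, and nothing is claimed about what it says.
- Open-label treatment is optional and need not be completed (sections 6.1 and 6.3). Participants whose provider thinks a treatment change is needed are withdrawn and encouraged to seek treatment (sections 1.3.3.3 and 1.3.3.8).
- Monitoring continues after the open-label dose. The open-label schedule has the C-SSRS at days 1, 7, 14, 21 and 28 after it, and section 1.3.3.8 provides for at least weekly contact.
- Section 6.2.6 treats visit timing as approximate, so 35-43 days is nominal and a late session would lengthen it.
- The number affected is unknown: only niacin participants who stopped an antidepressant and choose open-label. The whole arm is 15 as planned, or 18 if the 36 enrolled under section 9.2 are randomized evenly (36/2).

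**Conclusion.** The concern holds. The 1-2 weeks judged acceptable in section 1.3.3.8 is the scheduling wait, not the additional time off antidepressants. For a niacin participant who takes open-label psilocybin and stays on protocol, that time is nominally 35-43 days, with the earliest restart at day 64-71 after the first dose instead of Day 28-29.

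The range assumes the 7-14 day window starts on Day 28 and reads the decliner clause as Day 29; that reading moves the result by one day. The finding depends on neither choice, because the omitted four weeks follow directly from section 3.1.4. The defect is confined to the figure under the acceptability judgement; the restart rule and the monitoring are not faulted. It should be fixed, because an explicit safety judgement rests on a figure understated at least threefold.

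**What to change.** In the section 1.3.3.8 row, keep 1-2 weeks as the expected wait for the open-label session. State separately that, under section 3.1.4, the additional time off antidepressants is about 5-6 weeks (nominally 35-43 days), and restate the acceptability judgement for that whole interval. Support it with what the protocol already provides: weekly contact, the C-SSRS visits in the open-label schedule, the freedom to decline open-label, and withdrawal if treatment is needed. Use the same figure wherever the consent conversation gives a duration.

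In section 3.1.4, change the restart day for participants who decline open-label to one counted from the randomized dose. If the sponsor prefers to change the open-label restart rule, recompute the figure to match.

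The cost is a wording amendment to one table row and one clause, and a less favourable stated risk figure. If the restart rule is kept, visits, monitoring, endpoints and analysis are unchanged.

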1.3.4. Confidentiality

[figure not shown]
All participant records, paper or electronic, will be stored in locked offices and password-protected encrypted drives that will be accessible only to the principal investigator and other study personnel. Research databases will be coded (all identifiers except id number will be removed) during data analyses and are also kept on secure servers or encrypted computers.

We have requested from the FDA a Certificate of Confidentiality for this study to protect the identities of participants.

2. Study Design and Endpoints

2.1 Description of the Study Design

This is a randomized, double-blind, placebo-controlled study that offers participants randomized to the placebo arm the option to receive open-label psilocybin after primary outcome measurements have been completed.

2.2. Research Methods and Design

This study tests a hypothesis that a single session of psilocybin (the 'medication dosing' session) in the context of pre- and post-dose psychotherapy will result in improvement of symptoms of depression and burnout measured 4 weeks post-dose. This study hypothesis will be tested in a single site, double-blind, randomized controlled design involving 30 clinician participants that will compare effects of a single 25mg oral dose of psilocybin to a 100 mg of niacin (active placebo). The primary outcome measurements will be collected 4 weeks after

Page 16 Version 1.16, July 18, 2022

the psilocybin dose, after which the participant group assignment will be unblinded, and participants who received niacin will be offered the opportunity to have a second dose session with a 25 mg dose (with pre- and post-dose psychotherapy).

Precautions will be taken to reduce potential for COVID exposure, following FDA guidance (https://www.fda.gov/media/136238/download):

- Some psychotherapy sessions can be conducted by video, although at least one preparation session and one integration session will be done in person.
- COVID-19 screening procedures mandated by UW Medicine will be followed per UW Medicine policy. Currently UW Medicine policies require a basic symptom check before ambulatory care encounters, for example.
- Participants will be tested for COVID using a rapid antigen test on the morning
 of their medication session, and therapists will also be tested on the morning of
 the participant's medication session.
- Physical distancing will be maintained as much as possible.

2.3. Study Endpoints

2.3.1. Primary Endpoint

The primary endpoint will assess symptoms of depression using the Montgomery-Asberg Depression Rating Scale (MADRS), a clinician-assessed instrument, at 4 weeks post psilocybin-assisted psychotherapy vs control psychotherapy. We expect at least 50% of participants treated with psilocybin to have a 35% reduction in their MADRS compared to baseline, which is a clinically significant difference compared to the control arm.

2.3.2. Secondary Endpoints

- Assess symptoms of depression using the Montgomery-Asberg Depression Rating Scale (MADRS) prior to the primary endpoint at 1 week post psilocybin-assisted psychotherapy vs control psychotherapy.
- Assess symptoms of depression using the MADRS after psilocybin administration (for patients randomized to psilocybin or who receive open-label psilocybin) at 1 week, 4 weeks, 8 weeks, 12 weeks, and 6 months.
- Assess symptoms of burnout using the Stanford Fulfillment Index (SFI) at 4
 weeks post medication administration. We expect at least 50% of participants
 treated with psilocybin to show a reduction in the SFI work exhaustion and
 interpersonal disengagement subscales by at least 25% (from "a lot" to
 "moderately").
- Assess symptoms of burnout after psilocybin administration (for patients randomized to psilocybin or who receive open-label psilocybin) at 1 week, 4 weeks, 8 weeks, 12 weeks, and 6 months.
- Another secondary endpoint will assess symptoms of post-traumatic stress using the PCL5, measured at 1 week and 4 weeks after the medication session.
 We expect at least 50% of participants treated with psilocybin to show a reduction in PCL5 scores by at least 10 points (the clinically meaningful threshold for improvement).
- Assess symptoms of post-traumatic stress using the PCL5 after psilocybin administration (for patients randomized to psilocybin or who receive openlabel psilocybin) at 1 week, 4 weeks, 8 weeks, 12 weeks, and 6 months.
- A 10% or less difference in the rate of adverse events between the treatment and control arms at all study visits.

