3.1. Research Procedures

Participants will complete self-report and clinician-administered measures at baseline, prior to the medication dosing session, and at designated study visits (see figure next page).

Schedule for Activities during Randomized Phase									
Purpose	Screen	Prep	Prep	Medi- cation	Inte- gration	Inte- gration	Inte- gation	Follow -up	
Study day (approx)	-21-14	-7	-1	0	1	8	15	28	
Visit number		V1	V2	V3	V4	V5	V6	V7	
Research activity									
Demographics	X								
Eligibility Determination	X								
Medical exam	X								
Informed consent	X								
Caregiver contact info	X								
Blood draw	X								
Pregnancy screen (if applicable)	X			Х					
PI review of inclusion/exclusion	Х								

Page 18 Version 1.16, July 18, 2022

Informed Consent		X						
Mental health evaluation		Х						
Education re expectations	Х	Х						
Preparation psychotherapy		Х						
Urine screen	Χ							
Randomization				Х				
Medication (psilocybin or control)				Х				
Medication dosing monitoring				Х				
Integration psychotherapy					Х	Х	Х	
Adverse event reporting				Х	Х	Х	Х	
Un-blinding								X**
Measures								
Mont-Asberg Depression (MADRS)	Х	Х			Х	Х		Х
Beck Depression Scale		Х			X	Х		Х
Stanford Fulfillment Index		Х			X	Х		Х
Post-traumatic stress (PCL5)		Х			Х	Х		Х
Likelihood to leave job		Х			Х	Х		Х
Self-reported mystical exp				Х				
Moral injury symptom scale		Х						Х
Psychedelic Music Questionnaire					Х			
Psychological flexibility (AAQII)		Х				Х		Х
Interoceptive awareness (MAIA2)		Х			Х	Х		Х
Suicidality (C-SSRS)	Х	Х	Х	Х	Х	Х	Х	Х
Qualitative interview								Х
Adverse events, Suicidality	Х	Х	Χ	Х	X	Х	Х	Х

^{**}The unblinding will be done after the study coordinator has verified that the Day 28 measures have been completed.

Follow up measures for participants randomized to psilocybin							
Durance	Follow	Follow	Follow				
Purpose	-up	-up	-up				
Study day (approx.)	56	84	180				
Visit number	V8	V9	V10				
Measures							
Mont-Asberg Depression (MADRS)	Х	Х	Х				
Beck Depression Scale	Х	Х	Х				
Stanford Fulfillment Index	Χ	Х	Х				
Post-traumatic stress (PCL5)	Χ	Х	Х				
Likelihood to leave job	Χ	Х	Х				
Psychological flexibility (AAQII)	Χ	Х	X				
Interoceptive awareness (MAIA2)	Χ	Х	X				
Suicidality (C-SSRS)	Χ	X	X				
Qualitative interview							
Adverse events	Χ	Х	X				

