Findings of pregnancy, active cardiac medical issues, abnormal liver function, abnormal renal function, or abnormal blood counts, and any lab indicating an undiagnosed illness would exclude a participant from moving on to the preparation 1 visit. When screening requirements have been met, participants will have a visit with the PI and/or key study personnel in which the study, the scheduling and the procedures will be reviewed. All participants' questions will be answered prior to obtaining an informed consent.

After providing informed consent, the participant will complete initial measures. Note that randomization to the psilocybin or control (niacin) treatment groups will occur at the end of visit 2.

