Schedule for Activities during Open Label Psilocybin Phase										
Purpose	Prep	Medi- cation	Inte- gration	Inte- gration	Inte- gation	1 011011	Follow -up	Follow -up	Follow -up	Follow -up
Study day ('denotes open-label)	-1'	0'	1'	7'	14'	21'	28'	56'	84'	180'
Visit number	V7	V8	V9	V10	V11	V12	V13*	V14*	V15*	V16*
Research activity										
Psychiatric evaluation	Х									
Education re expectations	Х									
Preparation psychotherapy	Х									
Urine screen		Х								
Medication (psilocybin)		Х								
Medication dosing monitoring		Х								
Integration psychotherapy			Х	Х	Х					
Adverse event reporting		Х	X	X	X					
Measures										
Montgomery Asberg Depression	Х		Х	Х	Х	Х	Х	Х	X	
Beck Depression Scale	Х		Х	Х	Х	Х	Х	Х	X	
Stanford Fulfillment Index	Х		X	Х	Х	Х	Х	Х	Χ	
Post-traumatic stress (PCL5)	Х		Х	Х	Х	X	X	X	X	

Page 30 Version 1.16, July 18, 2022

Likelihood to leave job	Х				X					
Self-reported mystical exp		X								
Moral injury symptom scale		X						X		
Psychedelic music questionnaire			X							
Psychological flexibility (AAQII)	Χ				X	X	X	X	X	
Suicidality (C-SSRS)	Χ	X	X	X	X	X	X	X	X	X
Qualitative interview						X				
Adverse events	Х	X	X	X	X	X	X	X	X	

^{*}Note that V13, V14, V15, and V16 are likely to be video or remote visits.

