8.2. Time Period and Frequency for Event Assessment and Follow-Up

Adverse events will be reviewed with subjects weekly from the time of preparation visit 1 through primary outcome collect at 4 weeks. Information will be assessed in-person and during weekly phone calls. Adverse events or unanticipated problems involving risks to subjects or others will be reported to the HIC or HSC within 48 hours of it becoming known to the investigator, using the appropriate forms found on the website.

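### The 10% adverse-event endpoint is undefined, cannot be compared at every visit, and at about 15 per arm cannot show similar safety

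*Combined protocol and SAP*

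**What the plan says.** Section 2.3.2 lists as its last secondary endpoint "A 10% or less difference in the rate of adverse events between the treatment and control arms at all study visits". It does not say whether the rate counts participants, participant-visits or events. It also leaves open whether 10% is absolute or relative, whether direction matters, and whether the figure applies to a point estimate or a confidence bound. Section 9.2 gives methods only for mean change in MADRS, the Stanford Fulfillment Index and PCL5. The adverse-event endpoint is not in its testing hierarchy. Section 8 covers definition, grading, attribution and reporting of events, with no comparison between arms.

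On timing:
- Section 6.2.1 states that "randomization to the psilocybin or control (niacin) treatment groups will occur at the end of visit 2". The section 3.1 schedule marks randomization at V3.
- Under the same schedule, "The unblinding will be done after the study coordinator has verified that the Day 28 measures have been completed". V8-V10 (Days 56, 84 and 180) appear only in the table headed "Follow up measures for participants randomized to psilocybin", which lists adverse events at all three.
- The randomized-phase schedule has two event rows. "Adverse event reporting" is marked at V3-V6, and "Adverse events, Suicidality" is marked from screening to V7.
- Section 8.2 has events reviewed weekly from the first preparation visit until the 4-week primary outcome, and adds: "Information will be assessed in-person and during weekly phone calls".

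**The concern.** Most other secondary endpoints in section 2.3.2 say that something will be assessed. This one is worded as a result that is either achieved or not, yet the plan does not say how to decide which. The measure, the visits and the direction could all be chosen after the data are seen.

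It is also the only safety endpoint in section 2.3 and the only between-arm comparison of adverse events in the plan. A report that the criterion was met would naturally be read as evidence that the arms were similarly safe. A report that it was missed could be read as a signal of harm. The question is whether either reading would be justified with about 15 people per arm.

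**Working it through.** **1. The plan's own sizing.** The documents give no power, interval or sample size for this endpoint. The only sizing is for MADRS change: 1.06 and 1.23 SD units at 80% and 90% power with N=30. A two-sample t-test calculation (noncentral t, 15 per arm, two-sided 0.05) gives 1.060 and 1.226, so that table reproduces. The enrollment figure does too: 30/0.85 = 35.3, rounded up to 36. Neither figure bears on adverse events.

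**2. Where two randomized arms exist.**

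| Visits | Randomized comparison possible? |
|---|---|
| Screening, V1 | No, before allocation |
| V2 | No, or only after its end (section 6.2.1); the schedule says V3 |
| V3-V7 (dosing to Day 28) | Yes |
| V8-V10 | No, psilocybin arm only, after unblinding |

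**3. What 10% means in people.** Inputs: 15 per arm (sections 3.1.4 and 6.1), or 18 per arm if all 36 enrolled count (section 9.2). The reading used is an absolute difference in the proportion of participants with an event.
- 15 per arm: 1/15 = 6.7 points, 2/15 = 13.3 points.
- 18 per arm: 1/18 = 5.6 points, 2/18 = 11.1 points.

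Either way the arms may differ by at most one participant.

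**4. How often the rule is met.** With X1 and X2 independent binomials, P(met) is the sum of P(X1=i)P(X2=j) over all pairs with |i-j| of 1 or less. No event rate by arm is given, so the rates are assumptions.

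| True rates | 15 per arm | 18 per arm |
|---|---|---|
| Equal, 10% | missed 34.5% | missed 39.1% |
| Equal, 20% | missed 48.9% | missed 52.8% |
| Equal, 30% | missed 54.9% | missed 58.5% |
| Equal, 40% | missed 57.7% | missed 61.0% |
| Equal, 50% | missed 58.5% | missed 61.8% |
| 30% vs 10% | met 22.3% | met 16.8% |
| 40% vs 20% | met 23.5% | met 18.6% |
| 60% vs 40% | met 23.7% | met 19.3% |

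The rule is symmetric about 50%, so equal rates of 60% to 90% repeat the equal-rate rows. If only an excess on psilocybin counts as a miss, the equal-arm miss at 15 per arm halves, to 17.3% (10% rate) to 29.2% (50% rate).

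**5. What a result that meets the rule leaves open.** Take 5/15 against 4/15, a difference of 0.067. The Wilson 95% limits are 0.152 to 0.583 and 0.109 to 0.520. The Newcombe interval is then:
- lower: 0.067 - sqrt((0.333-0.152)² + (0.520-0.267)²) = 0.067 - 0.311, about -24 points;
- upper: 0.067 + sqrt((0.583-0.333)² + (0.267-0.109)²) = 0.067 + 0.295, about +36 points.

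At 15 per arm, 46 pairs of counts meet the rule. The smallest upper 95% limit among them is 14.4 points (0/15 against 1/15). At 18 per arm the smallest is 12.6 points. No qualifying result puts the upper 95% limit within 10 points.

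**The case against.** **The protocol does not claim similar safety.** This is correct. The endpoint is outside the formal hierarchy, and no halting or testing rule uses 10%. The investigator's review of event frequency and severity (section 8.11) does not depend on it either. A reader might infer a planned equivalence or non-inferiority claim, but the documents contain none. What stands is that a pass/fail criterion invites that conclusion when it is reported.

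**A between-arm comparison naturally applies only while both arms exist.** This is largely fair. Section 8.2 ends event review at 4 weeks, so V3-V7 is fully usable. It would be wrong to say that the endpoint fails at every visit. But the text says all visits, and the V8-V10 table still lists adverse events, so the wording needs correcting.

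**Other readings of the rate behave differently.** They do. Pooling participant-visits over V3-V7 gives 15 × 5 = 75 per arm. If visits were independent, the 95% half-width would be 1.96 × sqrt(2 × 0.1 × 0.9/75) = 9.6 points at a 10% rate and 16.0 points at 50%. So it cannot be said that every reading is less precise than the threshold. Visits within a person are unlikely to be independent, however, and nothing in the plan selects this reading.

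**Two further inferences should not be drawn.** "Schedule for Activities during Open Label Psilocybin Phase" reuses the numbers V7-V10, which might suggest that phases will be merged in tables. No section proposes tabulating by visit number alone, and that schedule is separately titled with its days marked as open-label. Nor do the documents say that the weekly calls in section 8.2 fall outside the study visits. The similar statement in section 1.3.3.3 concerns calls during antidepressant tapering.

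**Conclusion.** The endpoint is wrong as written. It has no defined measure, interval or method, and it asks for a comparison at visits where two randomized arms do not exist.

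On the participant-level absolute reading it also separates equal arms poorly from unequal ones. At 15 per arm, identical arms miss it 34.5% to 58.5% of the time, and a true 20-point excess meets it 22% to 24% of the time. At 18 per arm the ranges are 39% to 62% and 17% to 19%, so the conclusion is the same. Meeting the rule cannot support similar safety, and missing it does not show harm.

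These figures rest on assumed event rates of 10% to 50%, on that one reading, and on a single comparison. Failure to define the rate and failure to limit the visits do not depend on those assumptions. The consequence is confined to how safety is reported; the primary analysis and the stopping arrangements are unaffected.

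**What to change.** - Define the endpoint as the number and proportion of participants with at least one adverse event from dosing to Day 28, by arm, with the risk difference and a 95% interval (for example Newcombe). State the denominator.
- Report the same for moderate-or-worse, severe, serious and suicidality events. The event definition in section 8.1.1 is broad, and sections 1.3.3.1.b and 1.3.3.2 list common acute effects of both agents. If expected effects are counted, the any-event proportion may approach 100% in both arms and tell the reader little.
- Drop 10% as a success criterion, or keep it only as a descriptive benchmark beside the interval.
- Reconcile the two event rows in the randomized-phase schedule, and the V8-V10 entries, with the 4-week window in section 8.2. Reconcile the time of randomization between sections 6.2.1 and 3.1.
- Report V8-V10 and open-label events descriptively, separately by phase.

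The cost is wording, one table and corrected schedule rows. Severity, seriousness and C-SSRS are already collected, so no new assessment is needed. Each event needs a date or visit so that it can be placed in the window, which may mean one form field. The trial gives up a yes/no safety statement, which this sample size could not support. The interval does not add precision; it shows how little there is.
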